After Surveillance completion, patients will enter the Survival Follow-up period and will be followed per SOC, but information on off-protocol cancer treatment, recurrence and survival will be collected every 6 months for up to 3 years (see [Appendix 2](#)) after the patient receives the last dose of atezolizumab on study. Patients who discontinue the study due to adverse events will be followed until resolution or stabilization of the adverse event.

A schedule of activities is provided in [Appendix 1](#).

[figure not shown]
Figure 1 Study Schema

CT = computed tomography; MRI = magnetic resonance imaging; PET = positron emission tomography; PFT = pulmonary function test; SOC = standard of care.

^a Refer to [Appendix 2](#).

Figure 2 Surveillance Flow Chart with Treatment Subgroups

^a Total Surveillance period =2 years. If patient discontinues treatment for any reason, they should remain in Surveillance until they complete 2 years and then move to Survival Follow-up.

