3.1.4 Adjuvant Atezolizumab Therapy Phase

Patients whose tumors have evidence of pathologic response or lack of radiographic progression will be eligible for the Adjuvant Atezolizumab Therapy Phase, which will occur during the Surveillance period.

During this part of the study, patients will receive adjuvant atezolizumab for up to a maximum of 12 additional months (up to 18 cycles). Adjuvant atezolizumab treatment may be started directly after surgery or after adjuvant SOC chemotherapy (with or without radiation). Choice of adjuvant SOC chemotherapy will be at the discretion of the treating physician, depending on the disease stage, as deemed clinically appropriate. It is highly recommended that any adjuvant treatment be initiated within 120 days after surgery. Additionally, it is recommended that patients who receive SOC Chemotherapy (\pm Radiotherapy) initiate adjuvant atezolizumab within 60 days of SOC Chemotherapy \pm Radiotherapy (whichever occurs last). If adjuvant treatment is planned to start outside of the recommended window, *Investigators may discuss it with the Medical Monitor.*

Whole blood samples will be collected prior to infusion on adjuvant Cycle 1, Day 1. Subsequent blood samples will be collected during Surveillance (see Section 3.1.3) and 30 days after the last dose for correlative studies. The blood will be processed for PBMC, plasma, and serum.

Optional bronchial brushings samples may be collected from patients undergoing bronchoscopy or EBUS at prescreening or screening and approximately 3–4 months after starting adjuvant atezolizumab treatment (Group D only).

For all patients whose disease progresses or recurs (confirmed by imaging) at any time between neoadjuvant treatment and surveillance may undergo an optional tissue biopsy (tumor and lymph node, if available) for correlative studies, which will require a separate ICF signature (see Section 4.5.1). A blood sample will also be collected at the time of disease progression/recurrence.

All patients will enter Survival Follow-up, which will cover new anti-cancer treatment, DFS, and OS for up to 3 years after the last dose of atezolizumab (See [Appendix 2](#) for details regarding time in Survival Follow-up).

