Post-Surgery Visit / Surveillance Baseline	Surveillance 1 (S1) Visit	S2 Visit	Surveillance Assessments during SOC Chemotherapy	Surveillance Assessments during Adjuvant Atezolizumab	Assessments during Surveillance Only	Time in Survival Follow-Up ^a
(4–6 weeks after surgery)	6 weeks after Surveillance baseline (\pm 7days)	6 weeks after S1 Visit (\pm 7days)	N/A	See footnote ^b	See footnote ^d	–
Baseline Extended chest CT scan and blood sample for biomarker analysis	Blood sample for biomarker analysis	Extended chest CT scan and blood sample for biomarker analysis	N/A	Extended chest CT scan and blood sample collection for biomarker analysis; Optional bronchial brushings ^c	Extended chest CT scan and blood sample collection for biomarker analysis	Upon completion of surveillance, 2 years in Survival follow-up (until patients completes 3 years after last dose of adjuvant atezolizumab)

C=cycle; D=day; EBUS=Endobronchial ultrasound; SOC=standard of care; S=Surveillance (visit).

Notes: If visit is outside of the recommended window, please contact Medical Monitor for guidance and approval; if visit is outside of window, all indicated procedures should still be performed. Patients whose disease progresses or recurs during Surveillance will discontinue from Surveillance and enter Survival Follow-up.

^a If patients discontinues surveillance for any reason, patient will still be followed up for 3 years after last dose of atezolizumab treatment.

^b Below is guidance on how to synchronize the Surveillance and adjuvant atezolizumab treatment visits, however adjustments can be done as needed:

- If C1D1 performed within 6 weeks after Post-Surgery Visit/Surveillance Baseline, assessments can be synchronized with S1. Subsequent visits will follow the Surveillance schedule, with S2 approximately 6 weeks after S1 and subsequent visits (S3 to S9) at approximately every 3 months. Please note subsequent adjuvant cycles can also be adjusted to synchronize with Surveillance visits.

Appendix 2

Timing of Surveillance Assessments (cont.)

- If C1D1 is performed between 6 to 12 weeks after Post-Surgery Visit/Surveillance Baseline, C1D1 can be synchronized with S2. Subsequent assessments (S3 to S9) should be done approximately at every 3 months and can also be adjusted to synchronize with adjuvant atezolizumab cycles.

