- If first adjuvant atezolizumab cycle is performed >12 weeks after Post-Surgery Visit/Surveillance Baseline, C1D1 can be synchronized with S3. Subsequent assessments (S4 to S9) should be done approximately at every 3 months and can also be adjusted to synchronize with adjuvant atezolizumab cycles.
- ^c Optional Bronchial Brushings: will optionally be performed after approximately 3 to 4 months from the initiation of adjuvant atezolizumab (can be adjusted to synchronize with atezolizumab cycle). Bronchial brushings are highly encouraged for patients undergoing EBUS or bronchoscopy. See the laboratory manual for exact nomenclature and specific areas to be sampled during procedure
- ^d Upon completion/discontinuation of adjuvant atezolizumab treatment, patients will enter a Surveillance only period.
 - Treatment discontinuation visit will be performed 30 (± 5) days after last dose of adjuvant atezolizumab and a blood sample for biomarker assessment will be collected (see [Appendix 1](#)).
 - Surveillance Only assessments: First assessment (Extended chest CT scan and blood sample for biomarker analysis) will be done approximately 3 months after last dose of adjuvant atezolizumab and subsequent assessments approximately at every 3 months until the patient completes a total of 2 years in Surveillance (Adjuvant Atezolizumab + Surveillance = 2 years).

Appendix 2

Timing of Surveillance Assessments (cont.)

Table 3 Group C – SOC Chemotherapy (± Radiotherapy) Only

Post-Surgery Visit / Surveillance Baseline	Surveillance 1 (S1) Visit	S2 Visit	Surveillance Assessments during SOC Chemotherapy	Surveillance Assessments during Adjuvant Atezolizumab	Assessments during Surveillance Only	Time in Survival Follow-Up ^a
(4–6 weeks after surgery)	6 weeks after Surveillance baseline (± 7days)	6 weeks after S1 Visit (± 7days)	See footnote ^b	N/A	See footnote ^c	–
Baseline extended chest CT scan and blood sample for biomarker analysis	Blood sample for biomarker analysis	Extended chest CT scan and blood sample for biomarker analysis	Extended Chest CT scan and blood sample collection for biomarker analysis ^c	N/A	Extended chest CT scan and blood sample collection for biomarker analysis ^d	Upon completion of surveillance, until patient completes 3 years after last dose of neo adjuvant atezolizumab

C = cycle; D = day; SOC = standard of care; S = Surveillance (visit).

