Post-Surgery Visit / Surveillance Baseline	Surveillance 1 (S1) Visit	S2 Visit	Surveillance Assessments during SOC Chemotherapy	Surveillance Assessments during Adjuvant Atezolizumab	Assessments during Surveillance Only	Time in Survival Follow-Up ^a
(4–6 weeks after surgery)	6 weeks after Surveillance baseline (± 7days)	6 weeks after S1 Visit (± 7days)	See footnote ^b	See footnote ^c	See footnote ^d	–
Surveillance baseline chest CT scan and blood sample	Blood sample for biomarker analysis	Extended chest CT scan and blood sample for biomarker analysis	Chest CT scan and blood sample collection for biomarker analysis	Extended chest CT scan and blood sample collection for biomarker analysis	Extended chest CT scan and blood sample collection for biomarker analysis	Upon completion of surveillance, until patient completes 3 years after last dose of neoadjuvant atezolizumab

C=cycle; D=day; SOC=standard of care; S=Surveillance (visit).

Notes: If a visit is outside of the recommended window, please contact Medical Monitor for guidance and approval; all indicated procedures should still be performed. Patients whose disease progresses or recurs during Surveillance will discontinue from Surveillance and enter Survival Follow-up.

^a If patients discontinues surveillance for any reason, patient will still be followed up for 3 years after last dose of atezolizumab treatment.

^b SOC Adjuvant Chemotherapy/Radiotherapy cycles can be adjusted to synchronize with the Surveillance visits.

Below is guidance on how to synchronize the visits but adjustments can be done as needed.

- If C1D1 (chemotherapy) performed within 6 weeks after Post-Surgery Visit/Surveillance Baseline, it can be synchronized with S1. Subsequent visits will follow the Surveillance schedule, with S2 approximately 6 weeks after S1 and subsequent visits (S3 to S9) at approximately every 3 months. Please note subsequent adjuvant cycles can also be adjusted to synchronize with surveillance visits
- If C1D1 (chemotherapy) is performed between 6 to 12 weeks after Post-Surgery Visit/Surveillance Baseline, C1D1 can be synchronized with S2. Subsequent assessments (S3 to S9) should be done approximately at every 3 months and can also be adjusted to synchronize with adjuvant atezolizumab cycles.

Appendix 2

Timing of Surveillance Assessments (cont.)

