- If C1D1 (chemotherapy) cycle is performed > 12 weeks after Post-Surgery Visit/Surveillance Baseline, C1D1 can be synchronized with S3. Subsequent assessments (S4 to S9) should be done approximately at every 3 months and can also be adjusted to synchronize with adjuvant atezolizumab cycles.
- Upon completion of SOC Chemotherapy/Radiotherapy patients will move to adjuvant atezolizumab treatment for up to 12 months (maximum of 17 cycles). Extended CT scan needs to be done after completion of SOC adjuvant Chemotherapy/Radiotherapy and before initiation of adjuvant atezolizumab to rule out disease progression/recurrence. C1D1 (adjuvant atezolizumab) can be initiated within 60 days of last SOC Chemotherapy/Radiotherapy. If adjuvant treatment is planned to start outside of the recommended window, *Investigators may discuss it with the Medical Monitor*). All atezolizumab adjuvant cycles can be adjusted to synchronize with the surveillance visits.
- Upon completion/discontinuation of adjuvant atezolizumab treatment, patients will move to Surveillance only period. Treatment discontinuation visit will be performed 30 (± 5) days after last dose of adjuvant atezolizumab and blood sample for biomarker assessment will be collected (see [Appendix 1](#)).
 - Surveillance Only assessments: First assessment (Extended chest CT scan and blood sample for biomarker analysis) will be done approximately 3 months after last dose of adjuvant atezolizumab and subsequent assessments approximately at every 3 months until the patient completes a total of 2 years in Surveillance (Adjuvant Atezolizumab + Surveillance=2 years).

Appendix 3

Schedule of Biomarker Samples

Visit/Phase	Timepoint/Visit	Sample Type
Screening, Day -42 to -1	At visit	FFPE tumor tissue ^a
		Fresh frozen tumor tissue ^a
		Fresh lymph node (if available, highly encouraged)
		Bronchial Brushing (optional) ^b
		FFPE lymph node (optional, highly encouraged)
Atezolizumab Neoadjuvant Cycle 1, Day 1	Prior to infusion	Whole blood PBMC
		Whole blood flow cytometry
		Whole blood for serum and plasma biomarkers
		Whole blood for DNA
Surgery	Day of surgery (-7 to 1 day[s]) ^e	Whole blood PBMC
		Whole blood flow cytometry
		Whole blood for serum and plasma biomarkers
	At time of surgery	Fresh frozen tumor tissue surgical resection
		FFPE tumor tissue surgical resection

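### Appendix 2 Table 4 ends Survival Follow-up for Group D patients who complete Surveillance 3 years after the last neoadjuvant dose, although they go on to adjuvant atezolizumab

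*Protocol*

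**What the plan says.** Protocol Appendix 2 sets the time in Survival Follow-up separately for each adjuvant treatment subgroup.

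- **Table 4, Group D (chemotherapy, then adjuvant atezolizumab).** After Surveillance, follow-up runs "until patient completes 3 years after last dose of neoadjuvant atezolizumab". The notes to the same table say that after chemotherapy "patients will move to adjuvant atezolizumab treatment for up to 12 months (maximum of 17 cycles").
- **Table 4, footnote a.** "If patients discontinues surveillance for any reason, patient will still be followed up for 3 years after last dose of atezolizumab treatment". This covers only patients who leave Surveillance early.
- **Table 3, Group C (chemotherapy only).** "until patient completes 3 years after last dose of neo adjuvant atezolizumab". This group receives no adjuvant atezolizumab, so the neoadjuvant dose is its last dose.
- **Table 2, Group B (adjuvant atezolizumab only).** "2 years in Survival follow-up (until patients completes 3 years after last dose of adjuvant atezolizumab").

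The body of the protocol counts from the last atezolizumab dose. Section 3.1.1 collects follow-up for up to 3 years "after the patient receives the last dose of atezolizumab on study". Section 3.1.4 covers "DFS, and OS for up to 3 years after the last dose of atezolizumab" and then sends the reader to Appendix 2 "for details regarding time in Survival Follow-up". Section 4.5.6 counts from whichever of neoadjuvant or adjuvant treatment ends later. Section 3.2 expects the study to end about 3 years after the last adjuvant dose.

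**The concern.** Table 4 gives Group D in substance the Group C stopping rule, although on atezolizumab exposure Group D belongs with Group B. No reason is given for treating D differently from B, so this looks like text carried over from Table 3.

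The cell is an operative instruction. Section 3.1.4 directs a site to Appendix 2 for exactly this item, and a site that looks there finds the shorter rule. Footnote a does not rescue patients who complete Surveillance. It also creates an odd asymmetry: a Group D patient who finishes adjuvant treatment and then recurs during Surveillance is followed for 3 years from the last adjuvant dose, while one who completes Surveillance without recurrence is closed out earlier.

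At stake is late survival and recurrence information in patients given the longest treatment sequence in the study. The primary endpoint, major pathologic response, is not touched.

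**Working it through.** **Inputs from the documents**
- Last neoadjuvant dose (C2D1): Day 22 ± 3. Surgery: Day 40 ± 10 (Appendix 1).
- Post-surgery visit: 4 to 6 weeks after surgery, so Day 68 to 82. Surveillance ends 2 years after it (Section 3.2).
- Adjuvant dosing every 21 days. Seventeen cycles (Table 4) span 16 × 21 = 336 days from first to last dose; the 18 cycles in Section 3.1.4 would span 357.
- Recommended latest starts: any adjuvant treatment within 120 days of surgery, and atezolizumab within 60 days of chemotherapy (Section 3.1.4).

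**Assumptions.** The documents give no chemotherapy duration; I take 0 to 84 days from first to last chemotherapy dose. The earliest adjuvant start is taken as the 4-week post-surgery visit, Day 68. A month is 365.25/12 = 30.4375 days and 3 years is 1095.75 days.

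**Check on the plan's own figure.** Table 2 gives Group B 2 years of Survival Follow-up. With adjuvant treatment from Day 68, the last dose is Day 68 + 336 = 404 and follow-up ends on Day 404 + 1095.75 = 1499.75. Surveillance ends on Day 68 + 730.5 = 798.5. The difference is 701.25 days, or 23.0 months (1.92 years; 1.98 with 18 cycles). The stated 2 years is reproduced after rounding.

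**Loss in Group D.** Both rules add 3 years, so

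loss = last adjuvant dose day − last neoadjuvant dose day = (start + chemotherapy span + gap + 336) − 22.

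| First adjuvant treatment | Chemotherapy span (days) | Gap (days) | Loss (days) | Months |
|---|---|---|---|---|
| Day 68 | 0 | 0 | 68 + 336 − 22 = 382 | 12.6 |
| Day 68 | 63 | 21 | 68 + 63 + 21 + 336 − 22 = 466 | 15.3 |
| Day 68 | 63 | 60 | 68 + 63 + 60 + 336 − 22 = 505 | 16.6 |
| Day 160 (120 days after surgery) | 0 | 60 | 160 + 60 + 336 − 22 = 534 | 17.5 |
| Day 160 | 84 | 60 | 160 + 84 + 60 + 336 − 22 = 618 | 20.3 |

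The first row allows no chemotherapy. It is really a Group B timeline, so for a full course on nominal visit days it is a floor. Eighteen cycles would raise it to 403 days, 13.2 months. The visit windows move it between 30 + 28 + 336 − 25 = 369 days (12.1 months) and 50 + 28 + 336 − 19 = 395 days (13.0 months). Partial courses lose less: again with no chemotherapy time, eight doses give 40 + 28 + 147 − 22 = 193 days (6.3 months) and one dose gives 40 + 28 − 22 = 46 days (1.5 months).

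**What remains under the cell.** Follow-up ends on Day 22 + 1095.75 = 1117.75.
- Time in Survival Follow-up: 1117.75 − 798.5 = 319.25 days, 10.5 months (10.0 if the post-surgery visit is at 6 weeks), against about 2 years in Group B.
- By the SAP Section 6.3.3 duration formula, maximum OS and EFS follow-up is 1117.75/30.4375 = 36.7 months from first dose. Maximum DFS follow-up is (1117.75 − 40 + 1)/30.4375 = 35.4 months from surgery.

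**The case against.** The strongest reply is that Section 4.5.6 already states the right rule, and that Section 3.1.4 cites Appendix 2 for detail without saying it overrides the body. On that view a careful site keeps following the patient and nothing is lost. This stands in part: the loss is conditional on sites following the cell, and nothing in the documents shows that any patient was closed out early. But no text says which source prevails.

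Second, the body text says up to 3 years, which is a ceiling, and the Section 3.2 end-of-study date could be met by Group B patients alone. That is fair. Sections 3.1.1, 3.1.4 and 3.2 are out of line with the cell rather than flatly contradicted by it. The direct conflicts are with Table 2 and with the later-of-the-two rule in Section 4.5.6. Appendix 11 also uses that rule, but it is the Version 3 schedule for patients outside Surveillance, so I do not rely on it.

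Third, Group A is given only 1 year of Survival Follow-up, so a short period is not unusual. But Group A's last dose is neoadjuvant, so 1 year after Surveillance is roughly 3 years from last dose. That agrees with the general rule and does not support the Group D cell.

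Fourth, the analysis impact is small. SAP Section 6.3.3 runs Kaplan-Meier analyses on pooled populations and by pathologic response and PD-L1 status. Subgroups A to D serve for disposition (SAP Section 6.2.1), with no survival analysis planned by them. This stands.

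**Conclusion.** The Table 4 cell is wrong as written and should be corrected; the consequence is minor. If it is followed, a full-course Group D patient who completes Surveillance on nominal visit days loses at least about 12.6 months of follow-up. The loss is about 15 to 17 months under an assumed 63-day chemotherapy span from Day 68 with a 21 to 60 day gap, and up to about 20 months within the recommended windows with an assumed span of up to 84 days. Patients who discontinue Surveillance lose nothing, because footnote a applies.

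Three stronger readings are tempting, and the documents support none of them.
- **That 12.6 months is the typical Group D loss.** It allows no chemotherapy time, so it is a floor for a full course, and partial courses fall below it.
- **That the 36-month DFS estimate is lost,** because Group D follow-up stops at 35.4 months. The estimate is pooled, Group B patients can remain at risk beyond 36 months, and contacts about 6 months apart cannot resolve a 0.6-month shortfall. Group C has the same limit by design, and the OS and EFS landmarks are still reached. The effect is earlier administrative censoring in exploratory endpoints.
- **That follow-up has already been lost.** The documents do not show this. Nor do they give the size of Group D: Section 4.1 expects about 50 adjuvant patients in total. No patient-year total can be claimed.

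**What to change.** In Appendix 2 Table 4, change neoadjuvant to adjuvant in the Group D Survival Follow-up cell, so that it matches Table 2. Before the final OS, DFS and EFS analysis, check whether any Group D patient was closed out under the shorter rule. Where consent allows, resume 6-monthly contact for those patients.

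The correction removes the footnote a asymmetry. It does not break every link between recurrence and length of follow-up, because atezolizumab stops at progression (Section 4.6.2).

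The cost is an amendment with IRB/EC approval (Section 9.6). Patients already closed out may need re-consent: Appendix 1 footnote h treats the last Survival Follow-up visit as study completion, Section 8.2 calls for revised consent forms when procedures change, and the consent form itself is not available here. Each affected full-course patient needs about two to four extra contacts (382/182.6 = 2.1 to 618/182.6 = 3.4). Section 4.5.6 allows these by telephone, mail or email, so no added scans or clinic visits are needed.

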Appendix 5 **Pathological Response**

A detailed pathological evaluation will be performed on the surgically resected samples to obtain data described below.

Detailed pathological analysis will be performed for the post-treatment biopsies to determine the following:

1. Tumor size (3 measurements)
2. Tumor diagnosis using the 2015 World Health Organization (WHO) classification
3. Predominant differentiation of the tumor (well, moderately, or poorly differentiated), and for adenocarcinoma histology, the histology subtypes present
4. Lowest degree of tumor differentiation
5. Angiolymphatic invasion
6. Neural invasion
7. Margin status in mm
8. Degree of response International Union Against Cancer (UICC) pathological T and N stage
9. Total percentage of areas of necrosis
10. Total percentage of areas of fibrosis
11. Total percentage of viable tumor tissue
12. Total percentage of viable malignant cells
13. Evidence of field effect.

The pathology review will determine if the percentage of malignant cells after treatment is $\leq 10\%$, which is considered a major pathologic response (Hellmann et al. 2014).

Appendix 6

Response Evaluation Criteria in Solid Tumors, Version 1.1 (RECIST v1.1)

Selected sections from the Response Evaluation Criteria in Solid Tumors, Version 1.1 (RECIST v1.1), (Eisenhauer *et al.* 2009) are presented below, with the addition of explanatory text as needed for clarity.¹

MEASURABILITY OF TUMOR AT BASELINE

DEFINITIONS

At baseline, tumor lesions/lymph nodes will be categorized as measurable or non-measurable as follows.

a. Measurable Tumor Lesions

Tumor Lesions. Tumor lesions must be accurately measured in at least one dimension (longest diameter in the plane of measurement is to be recorded) with a minimum size of:

- 10 mm by CT or MRI scan (CT/MRI scan slice thickness/interval no greater than 5 mm)
- 10-mm caliper measurement by clinical examination (lesions that cannot be accurately measured with calipers should be recorded as non-measurable)
- 20 mm by chest X-ray

b. Non-Measurable Tumor Lesions

Non-measurable tumor lesions encompass small lesions (longest diameter < 10 mm or pathological lymph nodes with ≥ 10 to < 15 mm short axis), as well as truly non-measurable lesions. Lesions considered truly non-measurable include leptomeningeal disease, ascites, pleural or pericardial effusion, inflammatory breast disease, lymphangitic involvement of skin or lungs, peritoneal spread, and abdominal masses/abdominal organomegaly identified by physical examination that is not measurable by reproducible imaging techniques.

c. Special Considerations Regarding Lesion Measurability

Bone lesions, cystic lesions, and lesions previously treated with local therapy require particular comment, as outlined below.

Bone lesions:

- *Technetium-99m* bone scans, positron emission tomography (PET) scans, and plain films are not considered adequate imaging techniques for measuring bone lesions.

¹ For clarity and for consistency within this document, the section numbers and cross-references to other sections within the article have been deleted and minor changes have been made.

Appendix 6
Response Evaluation Criteria in Solid Tumors, Version 1.1 (RECIST v1.1)
(cont.)

- However, these techniques can be used to confirm the presence or disappearance of bone lesions.
- Lytic bone lesions or mixed lytic-blastic lesions, with identifiable soft tissue components, that can be evaluated by cross-sectional imaging techniques such as CT or MRI can be considered measurable lesions if the soft tissue component meets the definition of measurability described above.
- Blastic bone lesions are non-measurable.

Cystic lesions:

- Lesions that meet the criteria for radiographically defined simple cysts should not be considered malignant lesions (neither measurable nor non-measurable) since they are, by definition, simple cysts.
- Cystic lesions thought to represent cystic metastases can be considered measurable lesions if they meet the definition of measurability described above. However, if non-cystic lesions are present in the same patient, these are preferred for selection as target lesions.

Lesions with prior local treatment:

- Tumor lesions situated in a previously irradiated area or in an area subjected to other loco-regional therapy are usually not considered measurable unless there has been demonstrated progression in the lesion. Study protocols should detail the conditions under which such lesions would be considered measurable.

TARGET LESIONS: SPECIFICATIONS BY METHODS OF MEASUREMENTS

a. Measurement of Lesions

All measurements should be recorded in metric notation, using calipers if clinically assessed. All baseline evaluations should be performed as close as possible to the treatment start and *not usually* more than 4 weeks *prior to* the beginning of the treatment.

b. Method of Assessment

The same method of assessment and the same technique should be used to characterize each identified and reported lesion at baseline and during study. Imaging-based evaluation should always be the preferred option.

Clinical Lesions. Clinical lesions will be considered measurable when they are superficial and ≥ 10 mm in diameter assessed using calipers (e.g., skin nodules). For the case of skin lesions, documentation by color photography, including a ruler to estimate the size of the lesion is suggested.

Chest X-Ray. Chest CT is preferred over chest X-ray, particularly when progression is an important endpoint, *because* CT is more sensitive than X-ray, particularly in identifying

Appendix 6
Response Evaluation Criteria in Solid Tumors, Version 1.1 (RECIST v1.1)
(cont.)

new lesions. However, lesions on chest X-ray may be considered measurable if they are clearly defined and surrounded by aerated lung.

CT, MRI. CT is the best currently available and reproducible method to measure lesions selected for response assessment. *In this guideline, the definition of measurability of lesions on CT scan is based on the assumption that CT slice thickness is ≤ 5 mm. When CT scans have slice thickness > 5 mm, the minimum size for a measurable lesion should be twice the slice thickness.* MRI is also acceptable.

If prior to enrollment it is known that a patient is unable to undergo CT scans with IV contrast because of allergy or renal insufficiency, the decision as to whether a non-contrast CT or MRI (*with or without MRI IV contrast*) will be used to evaluate the patient at baseline and during the study should be guided by the tumor type under investigation and the anatomic location of the disease. For patients who develop contraindications to contrast after baseline contrast CT is done, the decision as to whether non-contrast CT or MRI (*with or without MRI IV contrast*) will be performed should also be based on the tumor type and the anatomic location of the disease and should be optimized to allow for comparison with the prior studies if possible. Each case should be discussed with the radiologist to determine if substitution of these other approaches is possible and, if not, the patient should be considered not evaluable from that point forward. Care must be taken in measurement of target lesions on a different modality and interpretation of non-target disease or new lesions since the same lesion may appear to have a different size using a new modality.

Ultrasound. Ultrasound is not useful in assessment of lesion size and should not be used as a method of measurement.

Endoscopy, Laparoscopy, Tumor Markers, Cytology, and Histology. The utilization of these techniques for objective tumor evaluation cannot generally be advised.

TUMOR RESPONSE EVALUATION

ASSESSMENT OF OVERALL TUMOR BURDEN AND MEASURABLE DISEASE

To assess objective response or future progression, it is necessary to estimate the overall tumor burden at baseline and to use this as a comparator for subsequent measurements. Measurable disease is defined by the presence of at least one measurable lesion, as detailed above.

BASELINE DOCUMENTATION OF TARGET AND NON-TARGET LESIONS

When more than one measurable lesion is present at baseline, all lesions up to a maximum of five lesions total (and a maximum of two lesions per organ) representative of all involved organs should be identified as target lesions and will be recorded and measured at baseline. This means in instances where patients have only one or two

Appendix 6
Response Evaluation Criteria in Solid Tumors, Version 1.1 (RECIST v1.1)
(cont.)

organ sites involved, a maximum of two lesions (one site) and four lesions (two sites), respectively, will be recorded. Other lesions (albeit measurable) in those organs will be recorded as non-measurable lesions (even if the size is >10 mm by CT scan).

Target lesions should be selected on the basis of their size (lesions with the longest diameter) and be representative of all involved organs but, additionally, should lend themselves to reproducible repeated measurements. It may be the case that, on occasion the largest lesion does not lend itself to reproducible measurement, in which circumstance the next largest lesion that can be measured reproducibly should be selected.

Lymph nodes merit special mention since they are normal anatomical structures that may be visible by imaging even if not involved by tumor. As noted above, pathological nodes that are defined as measurable and may be identified as target lesions must meet the criterion of a short axis of ≥ 15 mm by CT scan. Only the short axis of these nodes will contribute to the baseline sum. The short axis of the node is the diameter normally used by radiologists to judge if a node is involved by solid tumor. Nodal size is normally reported as two dimensions in the plane in which the image is obtained (for CT scan, this is almost always the axial plane; for MRI the plane of acquisition may be axial, sagittal, or coronal). The smaller of these measures is the short axis. For example, an abdominal node that is reported as being $20\text{ mm} \times 30\text{ mm}$ has a short axis of 20 mm and qualifies as a malignant, measurable node. In this example, 20 mm should be recorded as the node measurement. All other pathological nodes (those with short axis ≥ 10 mm but < 15 mm) should be considered non-target lesions. Nodes that have a short axis < 10 mm are considered non-pathological and should not be recorded or followed.

Lesions irradiated within 3 weeks prior to Cycle 1 Day 1 may not be counted as target lesions.

A sum of the diameters (longest for non-nodal lesions, short axis for nodal lesions) for all target lesions will be calculated and reported as the baseline sum of diameters. If lymph nodes are to be included in the sum, then, as noted above, only the short axis is added into the sum. The baseline sum of diameters will be used as a reference to further characterize any objective tumor regression in the measurable dimension of the disease.

All other lesions (or sites of disease), including pathological lymph nodes, should be identified as non-target lesions and should also be recorded at baseline. Measurements are not required and these lesions should be followed as “present,” “absent,” or in rare cases “unequivocal progression.”

In addition, it is possible to record multiple non-target lesions involving the same organ as a single item on the Case Report Form (CRF) (e.g., “multiple enlarged pelvic lymph nodes” or “multiple liver metastases”).

Appendix 6
Response Evaluation Criteria in Solid Tumors, Version 1.1 (RECIST v1.1)
(cont.)

RESPONSE CRITERIA

a. Evaluation of Target Lesions

This section provides the definitions of the criteria used to determine objective tumor response for target lesions.

- Complete response (CR): disappearance of all target lesions
 - Any pathological lymph nodes (whether target or non-target) must have reduction in short axis to < 10 mm.
- Partial response (PR): at least a 30% decrease in the sum of diameters of target lesions, taking as reference the baseline sum of diameters
- Progressive disease (PD): at least a 20% increase in the sum of diameters of target lesions, taking as reference the smallest sum on study (nadir), including baseline
 - In addition to the relative increase of 20%, the sum must also demonstrate an absolute increase of at least 5 mm.
 - The appearance of one or more new lesions is also considered progression.
- Stable disease (SD): neither sufficient shrinkage to qualify for PR nor sufficient increase to qualify for PD, taking as reference the smallest sum on study

b. Special Notes on the Assessment of Target Lesions

Lymph Nodes. Lymph nodes identified as target lesions should always have the actual short axis measurement recorded (measured in the same anatomical plane as the baseline examination), even if the nodes regress to < 10 mm on study. This means that when lymph nodes are included as target lesions, the sum of lesions may not be zero even if CR criteria are met, *given that* a normal lymph node is defined as having a short axis < 10 mm.

Target Lesions That Become Too Small to Measure. While on study, all lesions (nodal and non-nodal) recorded at baseline should have their actual measurements recorded at each subsequent evaluation, even when very small (e.g., 2 mm). However, sometimes lesions or lymph nodes that are recorded as target lesions at baseline become so faint on CT scan that the radiologist may not feel comfortable assigning an exact measure and may report them as being too small to measure. When this occurs, it is important that a value be recorded on the CRF as follows:

- If it is the opinion of the radiologist that the lesion has likely disappeared, the measurement should be recorded as 0 mm.
- If the lesion is believed to be present and is faintly seen but *is* too small to measure, a default value of 5 mm should be assigned and BML (below measurable limit) should be ticked. (Note: It is less likely that this rule will be used for lymph nodes since they usually have a definable size when normal and are frequently surrounded by fat such as in the retroperitoneum; however, if a lymph node is believed to be present and is faintly seen but *is* too small to measure, a default value of 5 mm should be assigned in this circumstance as well and BML should also be ticked.)

Appendix 6
Response Evaluation Criteria in Solid Tumors, Version 1.1 (RECIST v1.1)
(cont.)

To reiterate, however, if the radiologist is able to provide an actual measure, that should be recorded, even if it is below 5 mm, and, in that case, BML should not be ticked.

Lesions That Split or Coalesce on Treatment. When non-nodal lesions fragment, the longest diameters of the fragmented portions should be added together to calculate the target lesion sum. Similarly, as lesions coalesce, a plane between them may be maintained that would aid in obtaining maximal diameter measurements of each individual lesion. If the lesions have truly coalesced such that they are no longer separable, the vector of the longest diameter in this instance should be the maximal longest diameter for the coalesced lesion.

c. Evaluation of Non-Target Lesions

This section provides the definitions of the criteria used to determine the tumor response for the group of non-target lesions. Although some non-target lesions may actually be measurable, they need not be measured and, instead, should be assessed only qualitatively at the timepoints specified in the protocol.

- CR: disappearance of all non-target lesions and (if applicable) normalization of tumor marker level)
- All lymph nodes must be non-pathological in size (< 10 mm short axis).
- Non-CR/Non-PD: persistence of one or more non-target lesion(s) and/or (if applicable) maintenance of tumor marker level above the normal limits
- PD: unequivocal progression of existing non-target lesions
 - The appearance of one or more new lesions is also considered progression.

d. Special Notes on Assessment of Progression of Non-Target Disease

When the Patient Also Has Measurable Disease. In this setting, to achieve unequivocal progression on the basis of the non-target disease, there must be an overall level of substantial worsening in non-target disease in a magnitude that, even in the presence of SD or PR in target disease, the overall tumor burden has increased sufficiently to merit discontinuation of therapy. A modest increase in the size of one or more non-target lesions is usually not sufficient to qualify for unequivocal progression status. The designation of overall progression solely on the basis of change in non-target disease in the face of SD or PR of target disease will therefore be extremely rare.

When the Patient Has Only Non-Measurable Disease. This circumstance arises in some Phase III trials when it is not a criterion of study entry to have measurable disease. The same general concepts apply here as noted above; however, in this instance, there is no measurable disease assessment to factor into the interpretation of an increase in non-measurable disease burden. Because worsening in non-target disease cannot be easily quantified (by definition: if all lesions are truly non-measurable), a useful test that can be applied when assessing patients for unequivocal progression is to consider if the

Appendix 6
Response Evaluation Criteria in Solid Tumors, Version 1.1 (RECIST v1.1)
(cont.)

